## 1. Background and Rationale

Subacromial bursitis is a common cause of shoulder pain associated with functional limitation and reduced quality of life. Ultrasound-guided corticosteroid injections are widely used to reduce inflammation and pain, although their long-term effectiveness remains debated. Physiotherapy plays a key role in restoring shoulder function, but the optimal rehabilitation approach is still unclear. Proprioceptive Neuromuscular Facilitation (PNF) may enhance neuromuscular control and functional recovery. This study aims to evaluate the effectiveness of combining injections with different rehabilitation strategies.

## 2. Study Objective

To evaluate the effectiveness of ultrasound-guided corticosteroid injections combined with rehabilitation, and to compare PNF-based therapy with conventional physiotherapy in improving pain, function, and quality of life in patients with subacromial bursitis.

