## 3. Study Design

Randomized controlled trial with two parallel groups (1:1 allocation).

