## 4. Participants

Adults ( $\geq 18$  years) with chronic shoulder pain ( $\geq 3$  months) and pain intensity  $\geq 4$  on the Numeric Rating Scale (NRS).

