## 5. Intervention

All participants receive 3 weekly ultrasound-guided subacromial corticosteroid injections (triamcinolone acetate 40 mg + lidocaine).

After injections:

- Experimental group: PNF-based rehabilitation (10 sessions, 2 weeks)
- Control group: Conventional physiotherapy (10 sessions, 2 weeks)

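### Section 2's first aim, whether injections plus rehabilitation work, has no randomised contrast behind it; the design can test only PNF against conventional physiotherapy

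*Combined protocol and SAP*

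**What the plan says.** Section 2 (Study Objective) joins two aims. The first is "To evaluate the effectiveness of ultrasound-guided corticosteroid injections combined with rehabilitation". The second is "and to compare PNF-based therapy with conventional physiotherapy in improving pain, function, and quality of life".

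Section 3 (Study Design) describes a "Randomized controlled trial with two parallel groups (1:1 allocation"). Section 5 (Intervention) states that "All participants receive 3 weekly ultrasound-guided subacromial corticosteroid injections". After that course the arms diverge only in the kind of rehabilitation: "Experimental group: PNF-based rehabilitation (10 sessions, 2 weeks") and "Control group: Conventional physiotherapy (10 sessions, 2 weeks").

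Section 4 (Participants) requires pain of at least 4 "on the Numeric Rating Scale (NRS"), and Section 6 (Outcome Measures) makes the same scale the primary outcome, measured five times from baseline to 6 months. Section 7 (Statistical Analysis) names repeated measures ANOVA and independent t-tests at a 0.05 threshold. It does not say which test or which model term answers which aim.

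**The concern.** An effectiveness aim needs a comparator that lacks the thing being evaluated. For the first aim that would be an arm without the injections, without rehabilitation, or without both, and there is none. The only remaining evidence is how much participants change from baseline. That change mixes any treatment effect with spontaneous recovery, non-specific response to care and regression to the mean. Regression to the mean is built in, because people are selected for a high value on the scale later used to judge them.

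The risk lies in interpretation. A repeated measures ANOVA yields a time effect as well as a group-by-time interaction. With no analysis assigned to either aim, a significant time effect could be taken as the answer to the first aim, even if the two rehabilitation programmes do not differ. Section 1 describes the long-term value of these injections as unsettled, so readers may take such a result as evidence on that question.

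**Working it through.** **1. Match aims to contrasts.** This step needs no assumed figure.

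| Question | Randomised comparator in Sections 3 and 5 | What can inform it |
|---|---|---|
| Do the injections work? | None; both arms are injected | Change from baseline only |
| Does rehabilitation work? | None; both arms have 10 sessions over 2 weeks | Change from baseline only |
| Does the combination work? | None | Change from baseline only |
| PNF versus conventional physiotherapy | Yes, 1:1 | Group-by-time interaction, between-arm t-tests |

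There is one randomised contrast, and it serves the second aim. The post-injection assessment in Section 6 comes before rehabilitation, so change in the injection phase can be described separately. It is still an uncontrolled before-after change.

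**2. How large could regression to the mean be?** The documents state no mean, SD, correlation or sample size, so there is no plan figure to reproduce. What follows is an illustration. From the documents: entry threshold 4 and significance level 0.05 (taken as two-sided, since sidedness is not stated). Assumed: a continuous normal NRS before selection with mean μ of 4 to 7 and SD of 2, test-retest correlation ρ of 0.5 to 0.8, and 60 participants in total.

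Let c = (4 − μ)/SD and λ = φ(c)/(1 − Φ(c)). The expected fall with no treatment effect and no natural recovery is (1 − ρ) × SD × λ.

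| μ | c | λ | Fall at ρ = 0.5 | Fall at ρ = 0.8 |
|---|---|---|---|---|
| 4 | 0 | 0.798 | 0.5 × 2 × 0.798 = 0.80 | 0.2 × 2 × 0.798 = 0.32 |
| 5 | −0.5 | 0.509 | 0.51 | 0.20 |
| 6 | −1 | 0.288 | 0.29 | 0.12 |
| 7 | −1.5 | 0.139 | 0.14 | 0.2 × 2 × 0.139 = 0.06 |

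**3. How often would a before-after test be significant?** The variance of the change is SD² × [(1 − ρ)² v + 1 − ρ²], with v = 1 + cλ − λ². A normal approximation at the two extremes:

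- μ = 4, ρ = 0.5: v = 1 − 0.637 = 0.363. Variance = 4 × (0.25 × 0.363 + 0.75) = 3.36, so SD of change = 1.83 and SE = 1.83/√60 = 0.237. Ratio = 0.798/0.237 = 3.37. Probability ≈ Φ(3.37 − 1.96) = 0.92; simulating the paired t-test gives 0.91.
- μ = 7, ρ = 0.8: v = 1 − 0.208 − 0.019 = 0.773. Variance = 4 × (0.04 × 0.773 + 0.36) = 1.56, so SD of change = 1.25 and SE = 0.161. Ratio = 0.0555/0.161 = 0.34. Probability ≈ Φ(0.34 − 1.96) + Φ(−0.34 − 1.96) = 0.06; simulation also gives 0.06.

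The range is therefore roughly 6% to 90%. It depends heavily on inputs that nobody can read from the plan. At ρ = 0.6 the rate is about 83% for μ = 4, 45% for μ = 5, 17% for μ = 6 and 8% for μ = 7. If the NRS is scored in whole numbers from 0 to 10, the first two fall to about 67% and 30%. Natural recovery, where present, would raise all of these.

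**The case against.** Section 2 can be read as one comparative objective, with the first clause naming the treatment setting and the second the contrast. Section 1 supports this, since its sentence "This study aims to evaluate the effectiveness of combining injections with different rehabilitation strategies" fits what the two arms test. This carries some weight for Section 1, which needs no change. It does not rescue Section 2, where the linking words add the comparison as a further aim after the effectiveness aim.

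A reader might infer that the plan commits the sponsor to presenting a significant time effect as proof that the treatment works. The documents do not support that. Section 7 names no time-effect test, assigns no test to an aim and gives no rule of interpretation. What stands is weaker: nothing in the plan rules that reading out.

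A reader might also infer that a spurious before-after finding is close to a coin toss or worse. That follows only from particular choices, such as μ of 4 or 5 with ρ of 0.6. People presenting with chronic shoulder pain could plausibly have a higher mean, and then the excess over 5% is small. The design argument does not need these figures.

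Finally, it is fair to say that the harm depends on how results are later interpreted, and that the between-arm analysis is untouched. That bears on how serious the point is, and it is accepted.

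**Conclusion.** The point holds. Section 2 states an aim that the design cannot answer: there are no randomised contrasts for the injections, the rehabilitation or their combination, and one for PNF against conventional physiotherapy. This rests on Sections 2, 3 and 5 alone. The size of the possible misreading is uncertain: an expected fall of about 0.06 to 0.8 NRS points from selection alone, and a significant before-after test in roughly 6% to 90% of trials. Both ranges are conditional on the assumed SD, sample size, means and correlations above.

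This should be fixed before results are known. It does not invalidate the trial, because the second aim remains answerable from the randomised comparison. Nor do the documents justify dropping the word effectiveness altogether: it is legitimate for the comparison of the two rehabilitation programmes.

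**What to change.** - **Section 2:** make the confirmatory objective the comparison of PNF-based rehabilitation with conventional physiotherapy, both following the same injection course, on NRS. Keep change over time in the whole cohort, if wanted, as a descriptive aim.
- **Section 7:** state that efficacy conclusions rest on the between-group comparison (group-by-time interaction or between-arm difference). State that whole-cohort change from baseline will be given as a mean with 95% CI, is descriptive, and is not evidence that the injections, the rehabilitation or their combination work.
- **Section 1:** no change needed.

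The cost is rewording two sections, with no new participants, visits or arms and no change to treatment. The sponsor gives up a causal claim that the design could not have supported.

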## 3. Study Design

Randomized controlled trial with two parallel groups (1:1 allocation).

## 4. Participants

Adults ( $\geq 18$  years) with chronic shoulder pain ( $\geq 3$  months) and pain intensity  $\geq 4$  on the Numeric Rating Scale (NRS).

## 5. Intervention

All participants receive 3 weekly ultrasound-guided subacromial corticosteroid injections (triamcinolone acetate 40 mg + lidocaine).

After injections:

- Experimental group: PNF-based rehabilitation (10 sessions, 2 weeks)
- Control group: Conventional physiotherapy (10 sessions, 2 weeks)

## 6. Outcome Measures

- Primary: Numeric Rating Scale (NRS)
- Secondary: DASH, EQ-5D-3L, EQ-VAS, Range of Motion (ROM)

Assessments at baseline, post-injection, post-rehabilitation, 3 months, and 6 months follow-up.

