## **7. Statistical Analysis**

Data will be analyzed using repeated measures ANOVA and independent t-tests. A p-value  $<0.05$  will be considered statistically significant.

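### The arms cannot differ until after the second of five NRS visits, but Section 7 does not keep the two early visits off the outcome side or name an adjusted later-visit contrast

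*Combined protocol and SAP*

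**What the plan says.** Section 5 (Intervention) gives everyone the same first phase: "All participants receive 3 weekly ultrasound-guided subacromial corticosteroid injections". The randomised difference, PNF-based rehabilitation against conventional physiotherapy, begins only once the injections are complete.

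Section 6 (Outcome Measures) makes the NRS primary, names no primary time point, and lists the visits: "Assessments at baseline, post-injection, post-rehabilitation, 3 months, and 6 months follow-up".

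Section 7 (Statistical Analysis) gives the method in one sentence: "Data will be analyzed using repeated measures ANOVA and independent t-tests". A second sentence sets the significance level. Neither says:

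- which visits enter the ANOVA;
- whether the group main effect or the group-by-time interaction is the test;
- at which visit, or on what scale, the t-tests are done;
- whether any earlier score is a covariate.

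Section 2 (Study Objective) has two parts: the effect of injections combined with rehabilitation, and the comparison of the two rehabilitation programmes. Sections 3 and 5 do not say whether randomisation comes before or after the injections.

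**The concern.** Baseline and post-injection carry no information about a PNF effect when used as outcomes, because planned treatment is identical up to that point. They are valuable as predictors of each patient's later pain. Section 7 neither excludes them from the first role nor gives them the second.

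Three tests are open to the analyst, each with a different weakness for the comparison of the programmes:

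- **Group main effect over all visits.** Two visits with zero expected difference are averaged into the estimate.
- **Group-by-time interaction.** With five visits and two arms this is a 4-df test of whether the mean profiles are parallel. A significant result does not say which arm did better, by how much, or when.
- **Independent t-test at a later visit.** It estimates that visit's effect in full, but takes no account of the scores recorded before rehabilitation.

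Nothing rules out a between-arm t-test at baseline or post-injection either. Planned treatment gives no reason for a difference there, so a significant result would most naturally be chance.

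At stake are the precision of the primary comparison and whether its result can be stated as an effect of PNF on pain.

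**Working it through.** **Inputs from the documents.** There are five visits, two before the arms diverge and three after (Sections 5 and 6), and 1:1 allocation (Section 3). The documents state no sample size, SD, effect size or correlation, so there is no planned figure to reproduce.

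**Step 1: size of the dilution.** Let d3, d4 and d5 be the true differences at the three later visits.

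- Five-visit group main effect: (0 + 0 + d3 + d4 + d5)/5.
- Mean later effect: (d3 + d4 + d5)/3.
- Ratio: 3/5 = 60%, whatever the shape of the effect over the three visits.
- If baseline is left out and post-injection kept, the ratio is 3/4 = 75%.

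**Step 2: where the dilution does not apply.** A t-test at visit 3, 4 or 5 estimates d3, d4 or d5 in full. In the interaction, the early visits supply the contrast that shows the arms separating.

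**Step 3: illustrative power.** All inputs are assumed: n = 30 per arm, SD 2, d = 1 point at each later visit, correlation r = 0.5 between every pair of visits, two-sided 0.05. The signal is effect / (SD of the summary × √(2/30)), with √(2/30) = 0.258.

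| Test | Effect | SD of summary | Signal | Power |
|---|---|---|---|---|
| Five-visit main effect | 0.6 | 2√((1+4r)/5) = 1.549 | 1.50 | 31% |
| Three-visit main effect, unadjusted | 1 | 2√((1+2r)/3) = 1.633 | 2.37 | 65% |
| Single later visit, t-test | 1 | 2 | 1.94 | 48% |
| Single later visit, ANCOVA | 1 | 2√(1 − r²/((1+r)/2)) = 1.633 | 2.37 | 64% |
| Three-visit mean, ANCOVA | 1 | 2√((1+2r)/3 − r²/((1+r)/2)) = 1.155 | 3.35 | 91% |

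Both ANCOVA rows adjust for baseline and post-injection NRS.

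For the interaction, the squared deviations of (0, 0, 1, 1, 1) from their mean of 0.6 sum to 2 × 0.36 + 3 × 0.16 = 1.2. The noncentrality is (30/2) × 1.2 × (1/2)² / (1 − 0.5) = 9. On 4 and 232 df this gives 65%. A multivariate test gives about 62% and a simulation of the uncorrected test 67%, so the range is 62–67%.

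**Step 4: sensitivity to the correlation pattern.** If the correlation instead decays at 0.7 per visit step, the five-visit main effect stays at 31%, the interaction with Greenhouse-Geisser correction falls to 51%, and the three-visit-mean ANCOVA falls to 77%.

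**Step 5: sensitivity to a fading effect.** Return to r = 0.5 and let the effect be 1, 0.5 and 0.25 points. The mean is 1.75/3 = 0.583, the signal for the three-visit-mean ANCOVA is 0.583/(1.155 × 0.258) = 1.96, and power is about 49%. ANCOVA at the end of rehabilitation keeps 64%. In this scenario the two are equal when the mean later effect is 1.155/1.633 = 71% of the effect at the end of rehabilitation. Below that, the single visit is the stronger choice.

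**The case against.** The strongest reply is that Section 6 is only an assessment schedule and Section 7 never says that the two early visits are outcomes. A reader might infer that the plan commits to a five-visit main effect. It does not: that is one reading of an incomplete sentence. This part of the objection stands, so the 60% must be stated conditionally.

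A reader might also carry the 60% over to everything Section 7 names. Step 2 shows why that fails. The interaction is also the term usually of interest in a two-group repeated measures ANOVA, and under the assumptions above its 62–67% is about equal to simply dropping the two early visits (65%) or to ANCOVA at one visit (64%). The high power therefore belongs only to the adjusted three-visit mean with a sustained effect. Much of that gain comes from averaging and covariate adjustment, not from removing early visits. This also stands.

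Third, the early scores are needed as outcomes for the first part of the objective, the response to injections combined with rehabilitation. That is right, and the change below is limited to the comparison between programmes.

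None of this defends Section 7 as written. Under any reading it plans no stated adjustment for scores that are already collected, and it names no contrast that gives the direction and size of a PNF effect.

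**Conclusion.** The point holds in conditional form. That two of the five visits precede any planned difference between the arms follows directly from Sections 5 and 6. If the group main effect over all five visits is the test, its estimate is 60% of the mean later effect; this is arithmetic and needs no assumption about effect size or correlation.

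The power figures are illustrations on assumed inputs, and they depend on how long the effect lasts and how the scores correlate. Adjusting for the early scores beats the matching unadjusted test in the scenarios examined: at r = 0.5, 64% against 48% at a single visit and 91% against 65% for the three-visit mean. The choice between a single visit and the mean depends on how fast the effect is expected to fade.

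Using post-injection NRS as a covariate is sound whether randomisation comes before or after the injections, because planned treatment is the same until then. If randomisation comes first, this also requires that conduct during the injection phase does not differ by arm.

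This is a better use of data already scheduled for collection, so it goes beyond a request for missing detail.

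**What to change.** Amend Section 7 for the comparison of PNF with conventional physiotherapy:

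1. Make the primary analysis one prespecified between-arm contrast on NRS, either at one named visit from the end of rehabilitation onward or averaged over the three later visits. Give the reason for the choice, including how long the effect is expected to last.
2. Estimate it by ANCOVA or a mixed model with baseline and post-injection NRS as covariates, and report the difference with its confidence interval.
3. Do no between-arm significance tests at baseline or post-injection.
4. Keep the baseline and post-injection scores for a within-group description of change after the injections, which the first part of the objective needs.
5. State when randomisation takes place relative to the injections.

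The cost is a change of wording. No visit, measurement or participant is added. The choice should be fixed before any comparison by arm is seen.

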## **7. Statistical Analysis**

Data will be analyzed using repeated measures ANOVA and independent t-tests. A p-value  $<0.05$  will be considered statistically significant.

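### Pain on the NRS is the primary outcome, but no visit, ANOVA term or deciding method is fixed, so the unadjusted p<0.05 rule does not hold the primary comparison at 5%

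*Combined protocol and SAP*

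**What the plan says.** Section 6 lists NRS as the only primary outcome, with DASH, EQ-5D-3L, EQ-VAS and ROM as secondary. The schedule is "Assessments at baseline, post-injection, post-rehabilitation, 3 months, and 6 months follow-up", which gives four measurements after baseline. None is marked as primary.

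Section 7 is the whole analysis plan: "Data will be analyzed using repeated measures ANOVA and independent t-tests", with a p-value below 0.05 that "will be considered statistically significant". It does not specify:

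- which ANOVA term is of interest;
- how many t-tests are run, and at which visits;
- whether raw scores or changes from baseline are compared;
- whether the tests are two-sided;
- which method decides the primary question.

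It contains no multiplicity adjustment, testing order or gate, and no other section supplies one.

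Section 2 does name the randomized comparison: "to compare PNF-based therapy with conventional physiotherapy in improving pain, function, and quality of life". It also has a second aim: "To evaluate the effectiveness of ultrasound-guided corticosteroid injections combined with rehabilitation". Section 5 gives the injections to everyone ("All participants receive 3 weekly ultrasound-guided subacromial corticosteroid injections"), and the two rehabilitation programmes start only after them.

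**The concern.** Naming the outcome does not by itself define the primary hypothesis. On NRS alone, the text allows an ANOVA group effect, an ANOVA group-by-time effect and a t-test at each visit. These answer different questions. The group effect averages over visits, including any that precede the differing rehabilitation. The interaction asks whether the two time courses differ anywhere. A t-test asks about one visit. All are read against the same unadjusted threshold, and nothing in Section 7 prevents whichever falls below 0.05 from being presented as the primary result.

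At stake is what a positive finding would mean. If the visit and the test can be settled after the data are seen, a reader cannot tell a planned result from a selected one, and 0.05 is not the error rate of the trial's conclusion on pain.

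**Working it through.** **The plan's own figure.** The only error-rate figure is the per-test threshold of 0.05. There is no sample size, power statement or familywise level to reproduce.

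**Inputs from the documents.** Two arms, 1:1 (Section 3). Five assessments, four after baseline (Section 6). Three of those four follow the rehabilitation that differs between arms (Sections 5 and 6). Repeated measures ANOVA and t-tests, each at 0.05 (Section 7).

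**Assumptions, because the documents are silent.** 30 per arm; two-sided tests; normal scores with the same correlation between every pair of visits (0.3, 0.5 or 0.7); no true difference; raw scores; ANOVA over all five assessments; any significant test in the stated set counts as a positive result.

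**Independent-test bound.** For *k* independent tests at 0.05, the chance of at least one false positive is 1 − 0.95^k:

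- k = 3: 1 − 0.857 = 14.3%
- k = 4: 1 − 0.815 = 18.5%

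Repeated scores on the same patients are correlated, so the t-test figures should fall below these values.

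**Simulation.** 100,000 null trials per correlation; the entry is the proportion with at least one p<0.05 in the set.

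| Tests on NRS that count | corr. 0.3 | corr. 0.5 | corr. 0.7 |
|---|---|---|---|
| t-tests at all four post-baseline visits | 17.5% | 15.5% | 13.1% |
| The same, plus ANOVA group and interaction terms | 20.3% | 18.6% | 16.7% |
| t-tests at the three visits after rehabilitation | 13.6% | 12.4% | 10.9% |
| One t-test (6 months) plus interaction | 9.1% | 9.3% | 9.5% |
| One t-test only | 4.9% | 5.0% | 5.0% |
| Any of four t-tests, read only if the interaction is significant | 3.2% | 2.3% | 1.6% |

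**Sensitivity.** With 20 or 40 per arm and correlation from 0 to 0.9, including a pattern that decays with time:

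- four t-tests: 18.8% down to 9.4%;
- three t-tests after rehabilitation: 14.4% down to 8.4%;
- four t-tests plus both ANOVA terms: about 22% down to 13.5%;
- t-tests gated on the interaction: 0.8% to 4.2%.

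Arm size makes little difference. The number of tests, the gate and the correlation determine the result.

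**The case against.** The strongest reply is that no inflated error rate can be read off this plan. Section 7 does not say that t-tests are run at every visit, that any one significant result counts as success, or that the t-tests are read whatever the ANOVA shows. Under a conventional reading, with t-tests only as follow-up to a significant interaction, the rate is below 5%. This stands as a limit on the size. A reader might infer that the trial's false-positive rate on pain simply is 13 to 20%, and the documents do not support that. It is the result of particular readings combined with an unstated correlation. The reply does not remove the gap, because the reading that would protect the error rate is not written down either.

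Three further points on that side are sound:

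- The post-injection visit comes before the arms are treated differently, so only three visits bear on rehabilitation. Counting only those lowers the figure to about 11 to 14%, still more than double 5%.
- The comparison itself is not missing. Section 2 names PNF versus conventional physiotherapy. What is missing is the visit, the term and the deciding method.
- One might infer from Section 2 that pain, function and quality of life are co-equal, and add every secondary outcome to the count. Section 6 ranks them, so the secondary measures do not belong in an error rate for pain.

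One might also infer from Section 1 that 6 months must be the primary visit. The debated long-term effectiveness mentioned there is that of the injections, which both arms receive, so it does not settle the visit for a between-arm comparison.

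**Conclusion.** The concern holds as a gap in the plan, and it should be closed before the arms are compared. That no primary visit, model term or deciding method is fixed, and that the 0.05 threshold is unadjusted, is plain from Sections 6 and 7 and needs no assumption.

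The size is conditional on the assumptions listed with the calculation. Every reading examined in which more than one NRS test can count on its own, without a gate, exceeds 5%, from about 9% for one t-test plus the interaction to about 20% for four t-tests plus both ANOVA terms. The rate is 5% or less only with a single pre-specified test, a gate or an adjustment, and the plan states none of these. No single percentage should be quoted as the trial's actual error rate.

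**What to change.** Before any comparison of the arms, amend Sections 6 and 7 as follows.

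- **Primary test.** Name one: the between-arm difference in NRS at one visit after rehabilitation has been given, chosen by the sponsor from post-rehabilitation, 3 months and 6 months. State the one model that gives the p-value, at two-sided alpha 0.05. Any other method is a sensitivity analysis.
- **Secondary.** Place here the other NRS visits after rehabilitation, and DASH, EQ-5D-3L, EQ-VAS and ROM. Either test them in a pre-stated order, with the visit for each named, or report estimates with 95% confidence intervals and make no significance claims.
- **Post-injection visit.** Do not use it as evidence on rehabilitation, since the arms have been treated alike up to then.
- **Injections plus rehabilitation.** Both arms receive this combination, so this part of the objective can be seen only as change over time within groups. Report it descriptively.

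If the sponsor prefers to keep several visits as primary, a Bonferroni split over the three visits after rehabilitation (0.05/3 = 0.0167) would also hold 5%, with a stricter threshold at each visit.

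The cost is a few sentences, with no change to treatment or data collection. The downside is that a difference seen at only one other visit can no longer be called the primary result.

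### Section 7 names no analysis that adjusts for baseline; ANCOVA on the baseline score already collected would compare the arms more precisely than the planned t-tests

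*Combined protocol and SAP*

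**What the plan says.** Section 7 is the whole analysis plan. Its statement of method is one sentence: "Data will be analyzed using repeated measures ANOVA and independent t-tests". A second sentence sets the threshold at p < 0.05. The section does not say which method is primary, which outcome or visit each applies to, whether the t-tests take the follow-up score or its change from baseline, or which visits enter the ANOVA. It mentions no covariate, no ANCOVA and no mixed model.

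Section 6 makes the pain NRS primary, with DASH, EQ-5D-3L, EQ-VAS and range of motion secondary, and gives one schedule for them: "Assessments at baseline, post-injection, post-rehabilitation, 3 months, and 6 months follow-up". Section 5 shows that the first two of these five visits come before the arms' treatments differ: "All participants receive 3 weekly ultrasound-guided subacromial corticosteroid injections", and the two forms of rehabilitation follow. Neither Section 3 nor Section 5 says whether randomisation takes place before or after the injections.

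**The concern.** A baseline value of the same outcome is usually among the better predictors of its follow-up value. Used as a covariate in a randomised comparison, it removes explainable variance from the error term and corrects the estimate for whatever baseline difference chance has produced. A t-test on follow-up scores does neither. A t-test on change scores uses baseline, but with its coefficient fixed at 1 instead of estimated, so it over-corrects whenever r is below 1 (with equal SDs).

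Precision matters here because both arms receive the same injections and an active rehabilitation programme, so the difference between them may be modest. There is also a transparency issue. With the response of the t-test left open, follow-up, change and adjusted results would all be available once the data are in, and they can disagree.

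**Working it through.** **Inputs.** From the document: two arms, 1:1 (Section 3); two visits before the treatments differ and three after (Sections 5 and 6); significance at 0.05 (Section 7), taken as two-sided. The document gives no sample size, SD, target difference or correlation, so there is no planned figure to reproduce. Everything below rests on an assumed r and equal SDs across visits.

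**Step 1: one follow-up visit, baseline as the only covariate.** Variance of the estimated difference, relative to a t-test on follow-up scores (= 1), and the error left by a chance baseline imbalance D = 0.3 SD:

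| | Formula | r = 0.3 | r = 0.5 | r = 0.7 |
|---|---|---|---|---|
| Variance, change-score t-test | 2(1 − r) | 1.4 | 1.0 | 0.6 |
| Variance, ANCOVA | 1 − r² | 0.91 | 0.75 | 0.51 |
| Error, follow-up t-test (SD) | rD | 0.09 | 0.15 | 0.21 |
| Error, change-score t-test (SD) | (r − 1)D | −0.21 | −0.15 | −0.09 |
| Error, ANCOVA (SD) | about 0 | 0 | 0 | 0 |

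ANCOVA is never the less precise, apart from the degree of freedom it uses: 1 − r² ≤ 1, and 2(1 − r) − (1 − r²) = (1 − r)² ≥ 0. So whichever response the t-test was meant to have, ANCOVA does at least as well.

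**Step 2: power.** Assume 30 per arm, SD 2, a true difference of 1 point (0.5 SD) and two-sided 0.05.

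| | r = 0.3 | r = 0.5 | r = 0.7 |
|---|---|---|---|
| t-test on follow-up scores | 48% | 48% | 48% |
| ANCOVA, baseline only | 51% | 59% | 75% |
| ANCOVA, baseline and post-injection | about 51–52% | 63% | 82% |

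The last row uses the variance ratio 1 − 2r²/(1 + r) = 0.86, 0.67, 0.42. It needs both covariates, and it needs baseline to correlate with follow-up as strongly as the post-injection score does.

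**Step 3: the repeated measures ANOVA.** Suppose all five visits are time levels, correlations are compound symmetric at r, and the effect is constant over the three visits after rehabilitation. In units of one visit's variance, the mean of those three visits has variance (1 + 2r)/3 and the mean of the two earlier visits has (1 + r)/2.

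| | Formula | r = 0.3 | r = 0.5 | r = 0.7 |
|---|---|---|---|---|
| Later mean, unadjusted | (1 + 2r)/3 | 0.53 | 0.67 | 0.80 |
| Later mean minus earlier mean (group-by-time contrast) | (1 + 2r)/3 + (1 + r)/2 − 2r | 0.58 | 0.42 | 0.25 |
| ANCOVA on the earlier mean | (1 + 2r)/3 − r²/[(1 + r)/2] | 0.39 | 0.33 | 0.22 |
| ANCOVA on baseline only | (1 + 2r)/3 − r² | 0.44 | 0.42 | 0.31 |

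Given the same two earlier visits, ANCOVA is more precise than the contrast at each r. ANCOVA on baseline alone uses one visit fewer: it is better than the contrast at r = 0.3, level at 0.5 and worse at 0.7. Like for like, a contrast against baseline alone has (1 + 2r)/3 + 1 − 2r = 0.93, 0.67 and 0.40, again above the last row.

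If the group main effect were tested instead, the two early visits would dilute a constant effect to 3/5 of its size.

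**The case against.** The strongest objection is that the plan is under-specified and not demonstrably wrong. A reader might infer that the t-tests are on raw follow-up scores and that baseline is ignored. Section 7 does not say so: the response is unstated, and change scores would bring baseline in. A group-by-time term in the ANOVA would also use both early visits, and at higher r it recovers much of the gain (0.25 against 0.22 at r = 0.7 in Step 3). All of that stands. What it does not do is provide a reading under which the t-tests match ANCOVA, or under which the ANOVA contrast beats ANCOVA given the same early visits.

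A reader might also infer that chance imbalance biases the t-test. It does not. Over repeated randomisation the t-test is unbiased, and its standard error already allows for such imbalance. The error in Step 1 is conditional on the imbalance that happens to arise.

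The size of the gain is a fair target too. No correlation is given, and entry requires an NRS of at least 4 (Section 4), which truncates baseline pain and may lower its correlation with follow-up. At r = 0.3 the power gain is about 3 percentage points. The 63% and 82% figures should not be read as the return from baseline adjustment alone.

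Lastly, the post-injection score is not automatically a safe covariate. If allocation is made and known before the injections, that score, or dropout before it, could be influenced by allocation. The document does not settle this. Baseline adjustment is not exposed to this problem.

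**Conclusion.** The point holds as a matter of precision and specification. No baseline-adjusted analysis is named, although the plan collects what it needs. Relative to ANCOVA on baseline, a t-test on follow-up scores has 1/(1 − r²) = 1.10, 1.33 or 1.96 times the variance at r = 0.3, 0.5 or 0.7. A change-score t-test has 2/(1 + r) = 1.54, 1.33 or 1.18 times. These ratios assume equal SDs; the power figures further assume 30 per arm, SD 2 and a 1-point difference, and are illustrations only.

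The document does not support a claim that the planned tests are invalid, that the whole plan disregards the early measurements, or that a large power gain is assured. The change is worth making because it costs almost nothing, not because the t-test is in error.

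**What to change.** In Section 7, replace the independent t-tests with ANCOVA, or an equivalent mixed model: each outcome at a named analysis visit, regressed on arm and the baseline value of that outcome. Report the adjusted mean difference with its 95% confidence interval. Keep the unadjusted t-test as a sensitivity analysis and state whether it uses follow-up or change scores.

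State in Section 3 when randomisation and disclosure of allocation occur relative to the injections. Add the post-injection value as a second covariate only if one or the other takes place after that assessment.

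The cost is a few sentences and one degree of freedom, or two with the second covariate. No new data are needed. The change should be made before outcome data are seen by arm, so that the choice among follow-up, change and adjusted results is not open afterwards.
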